Subjects may withdraw voluntarily from participation in the study at any time and for any reason. Subjects may also be withdrawn on the basis of the Investigator's clinical judgment. This study may be terminated at the discretion of MedStar Health or of any regulatory agency for reasons including safety and/or treatment effect.

For enrolled subjects we anticipate that the main reasons for discontinuation of therapy will be either withdrawal of consent for continuation in the study or inability to tolerate the study. Other instances may include patient death, inability to take the study drug from severity of illness or inhospital complexity of illness. Subjective intolerance of the drug from minor side effects or alternatively cessation of COVID-19 related symptoms well ahead of the 28-day schedule may cause patients to want to discontinue the drug. With regards to drug toxicity itself, we anticipate minor symptomatology from adverse effects, such as headache, dizziness, nausea and vomiting, abdominal discomfort and rash (see also 1.4) based on prior human trial experience with the study drug. Should any subject dosed on the study drug experience seizures, which was reported as an

unrelated adverse event in an epilepsy trial, that individual would be subject to discontinuation out of an abundance of caution. Any emergent symptom that has no clear cause will result in a hold on subsequent study drug dosing until protocol assessment by the Study Investigator. The reasons for discontinuation of study drug will be documented clearly. In all cases study protocol monitoring will continue for the entire 60 days of the protocol as long as the subject stays consented.

When a subject withdraws or is withdrawn before completing the study, the date and reason for withdrawal are to be documented. Subjects who withdraw or who are withdrawn prematurely are to attend an early termination, at which time they will complete all assessments as outlined in the Schedule of Events (Table 1); moreover they will be encouraged to stay enrolled so that further safety and outcome information can be collected and analyzed.

In the event that a subject is withdrawn prematurely due to an adverse event or serious adverse event, the adverse event or serious adverse event will be followed until it resolves or stabilizes, or until it is judged by the Investigator to be no longer clinically significant.

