7.2 Instructions to Subjects

At enrollment, the Study Team will explain the subject diary (see Appendix) and ensure they understand what to enter in each field. They will be told about the importance of collecting the information in the diary for scientific purposes, and that even if they discontinue intake of the study drug, they should continue to participate in the study, continue to fill in the diary, and continue to attend planned study visits.

For outpatient subjects (and discharged former inpatient subjects), subjects will be instructed to take 3 tablets of IP at 0600, 1400, 2200 (+/- 4 hours) for up to 28 days. They will self-record administration of the IP in the subject diary to be reviewed by the study team who will assess compliance at each visit. The study team, under direction of the Investigator, will provide any needed medication education, including adequate storage requirements, with the subject and any relevant family member(s) or caretaker.

For subjects who become inpatients over the course of the trial, study medication will be supplied to the unit in which subjects are admitted and will be dosed by clinical nursing, recorded in the electronic medical record, and overseen by the study team. Doses will be given at 0600, 1400, 2200 (+/- 4 hours). Those who cannot swallow tablets will receive crushed tablets suspended in water and immediately administered through a nasogastric tube, by hospital nursing staff. As study medication will be administered by hospital staff, and there are no specific instructions to subjects. At discharge and subsequent outpatient visits, enough medication will be dispensed to the subject to assure they have adequate supply until their next on-site follow-up visit.

Women with a history of menstruation must agree to use effective method of contraception and protections that align with International Council on Harmonization M3 R2 guidelines for highly effective methods of contraception for the duration of the study (i.e., two forms of contraception, whereby one result in a less than 1 percent per year failure rate when used consistently and correctly), as well as to undergo additional pregnancy testing during the study on day 14. Details of all pregnancies in female participants will be collected for 60 days after randomization.

Warnings and Precautions

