7.5 Acute Conditions Brought on by COVID-19

The development of acute kidney and/or hepatic injury has been reported as a possible complication during the disease progression of COVID-19. Acute kidney and/or hepatic injury will be addressed in the following manner depending on whether at, (1) enrollment, (2) during the study period when drug is being administered in an ambulatory setting, (3) or during admission to hospital for COVID-19 related deterioration or other illness.

1. Potential participants in this study will undergo initial screening evaluation at a MedStar site or via a home health visit which includes background laboratory testing. If the testing indicates renal failure, GFR <30 or features of acute renal failure, most notably anuria, edema on examination in a previously healthy individual, the potential participant will not be enrolled as per the inclusion criteria or otherwise clarified with the nephrology consultant managing the patient. Similarly, potential participants shown to have evidence

of elevated liver function tests (determined by ALT, AST, GGT, or ALP >2 x upper limit of normal, and/or total Bilirubin > upper limit of normal) will not be enrolled in the study.

- 2. Laboratory testing throughout the study period (see Section 5.2 Table 1) may, though unlikely, show an acute change in renal or liver testing to indicate acute organ-specific disease or involvement as a possible complication of COVID-19. In such a circumstance, subjects will be directed to seek care from the respective hospital/specialist. In the case of acute liver injury with functional impairment, the IP will be discontinued immediately after blood has been taken for future assessment of drug levels. In the case of subjects with elevated liver function tests suggestive of acute liver injury without functional impairment, IP will be held to discern in the first instance the possibility of an adverse event and restarted in consultation with the managing hepatologist if it is determined to be COVID-19 related hepatopathy. In the case of subjects with acute renal injury, IP will be held to discern in the first instance the possibility of an adverse event and restarted in consultation with the managing nephrologist if it is determined to be COVID-19 related nephropathy. DSMB guidelines for unblinding will be followed in these cases as relevant.

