7.7 Laboratory Abnormalities

Clinical labs will be performed locally at WHC or other MedStar clinical sites. Labs to be drawn during the study include serum chemistries, a hematology panel and an immune panel (see Appendix 12.1 for more details). A serum pregnancy test must be performed, and the result must be negative prior to the entry of women of child-bearing potential.

Clinical laboratory reports must be reviewed by a physician for out-of-range values within 12 hours of receipt. Out-of-range values will be evaluated using the following notations:

- NCS: Not clinically significant
- LE: Laboratory Error
- PT: Subject abnormal; relates to the subject's usual state of health
- CS: Clinically Significant. This value cannot be explained by any of the other indicators.

By definition a lab value flagged as "CS" indicates an adverse event and will be captured on the CRF. A laboratory test flagged "CS" should be repeated as soon as possible, then the Investigator should use his or her judgment as to whether the abnormal finding is sufficient reason to immediately withdraw the subject from the study.

If a laboratory value is considered to be serious and life-threatening and at least possibly related to the study drug, the subject should be immediately discontinued from the study and appropriate therapy started. Refer to Sections 7.8 to Section 7.13 for definition of a serious adverse event and related terms, and details on reporting a serious adverse event.

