8 DATA MANAGEMENT AND STATISTICS

8.1 Populations for Analyses

The following populations will be considered for statistical analyses.

• Safety & Tolerability Population: All enrolled subjects who have received at least 1 dose of IP (belnacasan or placebo) will be studied. Even if subjects have discontinued study treatment, as long as they maintain consent, they will continue to be in the study and

included in analysis, i.e., their safety and tolerability information will continue to be collected for at least 60 days.

• *Treatment Effect Evaluable Populations*: All enrolled subjects who have received at least 1 dose of IP (belnacasan or placebo) will be studied. Even if subjects have discontinued study treatment, as long as they maintain consent, they will continue to be in the study and included in analysis, i.e., their outcome information will continue to be collected for at least 60 days.

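### Sections 7.9 and 7.10 end adverse event collection 28 days after the last dose, short of the day-60 primary endpoint; the withdrawal wording in 7.7 needs a matching edit

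*Combined protocol and SAP*

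**What the plan says.** **The day-60 horizon.** Section 3.2 assesses the primary endpoint, incidence of adverse events (AEs) and serious adverse events (SAEs), out to day 60. Section 8.4 counts those events to 60 days from randomization in a Poisson model, with subject follow-up time as exposure. Section 7.8 has AEs recorded for the duration of the study, and the AE assessment row of Table 1 is marked at days 42 and 60. Section 5.3 states: "In all cases study protocol monitoring will continue for the entire 60 days of the protocol as long as the subject stays consented". Section 8.1 says of subjects who have stopped treatment but remain consented that "their safety and tolerability information will continue to be collected for at least 60 days". Section 7.2 tells subjects who stop the drug to "continue to participate in the study, continue to fill in the diary, and continue to attend planned study visits".

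**The shorter window.** Section 7.9 requires recording of AEs that begin between the first dose and 28 days after the last dose. Section 7.10 collects AEs and SAEs over the same span.

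**The withdrawal wording.** For a serious, life-threatening laboratory value that is at least possibly related to study drug, section 7.7 says "the subject should be immediately discontinued from the study and appropriate therapy started". For a repeated clinically significant value, the investigator judges whether "the abnormal finding is sufficient reason to immediately withdraw the subject from the study". By contrast, section 7.5 stops only the drug ("the IP will be discontinued immediately after blood has been taken" in acute liver injury with functional impairment), and the liver rules at the end of 7.7 speak of stopping treatment.

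**The concern.** AE/SAE incidence is the primary endpoint, so the collection window defines the primary data. Two windows are in force, and the shorter is tied to the last dose, not to randomization. The loss under it therefore grows the earlier a subject stops. If tolerability differs between arms, the amount of uncollected time differs between arms as well.

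Section 8.4 does not say whether follow-up time means time in the study or time under AE collection. A subject who stops drug on day 7 and takes the day-60 call could contribute 60 days of exposure with only 35 days of recorded events.

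The 7.7 wording adds a smaller problem. Taken literally, it ends follow-up in subjects with suspected toxicity, against the commitments in 5.3 and 8.1.

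**Working it through.** The plan states no figure for this point. The power statement in 8.7 does not depend on it and does not change.

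**Inputs.** Last planned dose on day 28 (5.1). Window of 28 days after the last dose (7.9, 7.10). Endpoint and analysis horizon of day 60 (3.2, 8.4). 20 subjects per arm, 40 in all (8.7). The stop days 7, 14 and 21 are illustrations placed at scheduled visits. Day 1 is taken as both randomization and first dose.

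**Step 1: the window.** Window end = last dose day + 28. Shortfall = 60 − window end.

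| Last dose day | Window ends | Shortfall | Share of 60 days |
|---|---|---|---|
| 28 | 28 + 28 = 56 | 4 | 6.7% |
| 21 | 21 + 28 = 49 | 11 | 18.3% |
| 14 | 14 + 28 = 42 | 18 | 30.0% |
| 7 | 7 + 28 = 35 | 25 | 41.7% |

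These are upper ends of a range. If sites follow 7.8 and Table 1, every shortfall is 0. If all 40 subjects complete dosing and follow-up and sites apply 7.9/7.10 strictly, the total is 4 × 40 = 160 of 40 × 60 = 2,400 person-days, or 6.7%.

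**Step 2: effect on the incidence rate ratio (IRR).** Assume a true IRR of 1, a constant event rate, exposure entered as 60 days for everyone, all placebo subjects completing, and a share s of the belnacasan arm stopping on day 7. Then expected IRR = [(1 − s) × 56 + s × 35] / 56.

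- s = 10% (2 of 20): (50.4 + 3.5) / 56 = 0.96
- s = 25% (5 of 20): (42.0 + 8.75) / 56 = 0.91
- s = 40% (8 of 20): (33.6 + 14.0) / 56 = 0.85

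If exposure is cut at the window end (35 or 56 days), numerator and exposure shrink together. Under a constant rate the expected IRR returns to 1, but events after the cut are still not counted. With more early stoppers on placebo, the bias in the first case reverses.

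**Step 3: section 7.7 alongside the window.**

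- 7.7 read as stopping study drug: it removes no follow-up.
- 7.7 read literally, 7.9/7.10 unchanged: collection of new events ends at the stop instead of 28 days later (35 − 7 = 42 − 14 = 49 − 21 = 28). That is up to 28 further days per affected subject, or 28 / 1,200 = 2.3% of the arm's person-days.
- 7.7 read literally, 7.9/7.10 moved to day 60: the loss after a stop on day 7, 14 or 21 is 60 − 7 = 53, 60 − 14 = 46 or 60 − 21 = 39 days.
- 7.7 corrected, 7.9/7.10 unchanged: 25, 18 or 11 days can still be lost.

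Neither edit alone closes the gap under every reading.

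**The case against.** The best defence is that the rest of the protocol points to day 60. Sections 3.2, 7.8 and 8.4 and the AE row of Table 1 agree, and 7.9 sets what must be recorded without forbidding later entries. For a completer the gap is only days 57 to 60, with an AE assessment scheduled on day 60. Section 8.4 also foresees follow-up shorter than 60 days and carries follow-up time as exposure. All of this stands, and it is why each range starts at 0. A reader might infer that AE recording certainly ends at day 56 for everyone; the documents do not support that. They hold two instructions, and the end point stated in 7.10 contradicts the day-60 endpoint.

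A reader might also infer that 7.7 removes the most informative safety subjects from the trial. The text does not carry that either. Section 5.3 continues monitoring in all cases while consent holds. For subjects who are withdrawn it adds an early termination visit and says "moreover they will be encouraged to stay enrolled so that further safety and outcome information can be collected and analyzed". Section 5.1 uses nearly the same phrase for subjects who only stop drug, and note 10 to Table 1 ties the early termination visit to stopping drug. After a withdrawal for an adverse event, "the adverse event or serious adverse event will be followed until it resolves or stabilizes". The second 7.7 sentence is discretionary. So 7.7 is most plausibly loose wording for study drug. What remains is that its words conflict with 5.3 and 8.1, and that following the triggering event does not cover new events.

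Nor should it be assumed that the triggering event always enters the 3-of-20 safety rule. Section 8.4 counts only grade 4 or 5 SAEs judged probably related, whereas 7.7 acts at possibly related.

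**Conclusion.** The inconsistency is real and should be corrected. Sections 7.9 and 7.10 set an AE/SAE window that ends before the day-60 primary endpoint. The possible loss is 0 to 4 days per completer and 0 to 25, 18 or 11 days after a stop on day 7, 14 or 21, depending on which instruction sites follow.

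The direction of any effect on the IRR is unknown, because the documents do not say how many subjects will stop early or in which arm. The values 0.96, 0.91 and 0.85 are illustrations under the assumptions stated with them, not predictions. The wording of 7.7 is a secondary matter: it loses nothing if read as study drug, and the number of subjects it would touch is unknown.

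**What to change.** In 7.9 and 7.10, set AE/SAE collection to run from first dose to day 60, or to 28 days after the last dose if that is later, for every dosed subject whatever the last dose day, unless consent is withdrawn. This matches 3.2, 7.8, 8.4 and Table 1.

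In both 7.7 sentences, replace withdrawal or discontinuation from the study with discontinuation of study drug, with scheduled visits, laboratory tests and AE/SAE collection continuing to day 60 unless consent is withdrawn. This matches 5.3, 8.1, 7.5 and the liver rules.

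The cost is one sentence each in 7.9 and 7.10 and two in 7.7. The visits, laboratory tests and the day 42 and 60 calls are already scheduled for every subject, and the sample size does not change.

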5 STUDY DESIGN

5.1 Study Description

This is a phase 2 proof of concept randomized, double-blind, placebo-controlled trial with the purpose of assessing the safety, tolerability and treatment effect of the orally administered Caspase-1 inhibitor, belnacasan, for the treatment of patients with mild to moderate COVID-19. 20 subjects will be given 900 mg TID of belnacasan and 20 subjects will be given a placebo TID for 28 days, and assessments of safety, tolerability, and treatment effect will be performed for up to 60 days.

At the screening / baseline / day 1 Visit, subjects will provide informed consent and be screened for eligibility based on the Inclusion / Exclusion criteria identified in Section 5.3. Subjects will also receive the first dose of study drug at this visit once study eligibility has been confirmed, and the second dose of study drug will be taken approximately 8-12 hours after the first dose. Study drug will be continued three times daily (morning, mid-day, and nighttime doses) through day 28. Some patients identified will require a PCR-confirmed COVID test, having only had a rapid antigen test. Patients requiring a PCR test can either have one collected with screening labs prior to leaving the MedStar enrollment site or have these labs collected via a home-health research visit at no cost to the potential participant. Prior to study-specific procedures the study team will obtain their consent in-person or by remote consent process. An e-consent platform, Interlace, may also be used to document consent electronically. Once their COVID-19 status is confirmed via PCR they will complete the remainder of their screening/enrollment visit at either MedStar Washington Hospital Center or MedStar Franklin Square within the next 1 to 3 days. The remote consent

process and e-consent will follow MedStar institutional policies and procedures (MG.O-004.06 and MG.O-004.07).

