The trial duration will be approximately 60 days (8.5 weeks) for all subjects enrolled. As outlined in the Schedule of Events Table in Section 5.2, over the course of the study duration, all subjects will use a diary to record IP intake as well as symptoms and activity levels with guidance to do so at the same time each day; assess physical parameters using a study-provided thermometer and pulse oximeter for which detailed instructions will be provided at enrollment; be assessed at regular intervals by the Study Team via telephone calls and in-person follow-up clinic visits; and give blood for laboratory tests.

An experienced and appropriately licensed Study Team member will conduct the telephone study visits and be the point of contact if subjects experience deterioration, such as high temperatures (above 38C) or low oxygen saturation levels (below 93%). The primary coordinator of the trial will be a registered nurse, experienced in vital sign and symptom review, with the ability to escalate any medical concerns to the Principal Investigator as it relates to worsening of the subjects' illness or adverse event identification. The Principal Investigator or delegated Sub-Investigator, as documented on the study delegation log, is well-versed in delegation of appropriate tasks as defined by licensure and scope of practice and will work closely with the study team to assure delegation remains appropriate through the duration of the trial. Medical advice or direction will only be given by sufficiently licensed study personnel, either mid-level providers or physicians, in partnership with their primary care team.

Subjects will be instructed to fill in symptoms assessment, overall health assessment, temperature and oxygen saturation levels in the diary each morning; and to note in the diary 3 times per day that they have taken the study drug. The Study Team will conduct in-person visits with the subjects on days 7, 14, 21, and 28 and telephonic visits with subjects on days 1, 4, 10, 42, and 60; as well as when / if subjects contact them due to symptom deterioration as instructed. Subjects will receive reminders to complete the diary via text message and / or email. Subjects who prematurely discontinue study drug for any reason will be asked to have an Early Termination (ET) visit the day the last study drug dose is administered; moreover, they will be encouraged to stay enrolled so that further safety and outcome information can be collected and analyzed.

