Particular attention will be paid to determine the possibility of drug induced liver injury (DILI) as detailed in the FDA guidance document "Drug-Induced Liver Injury: Premarketing Clinical Evaluation." Liver tests (ALT, AST, ALP, and total Bilirubin) will be performed at enrollment and at days 7, 14, and 28 throughout the drug administration period. For patients exhibiting signs of liver disease such as fatigue, nausea, vomiting, right upper quadrant pain or tenderness, fever, or rash, extensive laboratory testing will be performed that includes above liver chemistries immediately. Otherwise, on routine weekly testing an increase of serum aminotransferase levels to >3x upper limit of normal would automatically trigger repeat testing within 48 to 72 hours of all four of the usual serum measures (ALT, AST, ALP, and total Bilirubin) to confirm the abnormalities and to determine if they are increasing or decreasing. If symptoms and/or aminotransferase levels remain >3x upper limit of normal, the participant will be monitored more

closely with lab schedule, in-person or virtual evaluation twice weekly or more. A thorough evaluation for additional causes of liver test anomalies will be conducted in consultation with Hepatology. A case report form page will be created and DSMB review triggered. Otherwise, discontinuation of treatment will be considered immediately if:

- ALT or AST >8x upper limit of normal
- ALT or AST >5x upper limit of normal for more than 2 weeks
- ALT or AST >3x upper limit of normal and total Bilirubin >2x upper limit of normal or INR >1.5
- ALT or AST >3x upper limit of normal with the appearance of fatigue, nausea, vomiting, right upper quadrant pain or tenderness, fever, rash, and/or eosinophilia (>5%).

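### Section 7.7 assumes weekly liver tests but none is scheduled on day 21, so a new symptom-free rise after day 14 is first seen on the last dosing day

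*Combined protocol and SAP*

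**What the plan says.** Section 7.7 fixes the liver-test days: "Liver tests (ALT, AST, ALP, and total Bilirubin) will be performed at enrollment and at days 7, 14, and 28". A few lines later its trigger rests on a different schedule. The condition is "on routine weekly testing an increase of serum aminotransferase levels to >3x upper limit of normal", and such a rise "would automatically trigger repeat testing within 48 to 72 hours of all four of the usual serum measures".

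Two provisions can then stop or pause dosing:

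- **Section 7.7:** "discontinuation of treatment will be considered immediately if" any of four thresholds is met. They are: above 8x ULN; "ALT or AST >5x upper limit of normal for more than 2 weeks"; above 3x ULN with raised bilirubin or INR; and above 3x ULN with listed symptoms or eosinophilia.
- **Section 7.5:** for subjects with "elevated liver function tests suggestive of acute liver injury without functional impairment, IP will be held" while the cause is worked out.

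On timing, Section 5.1 says "Study drug will be continued three times daily (morning, mid-day, and nighttime doses) through day 28" and "The Study Team will conduct in-person visits with the subjects on days 7, 14, 21, and 28". In Table 1 (Section 5.2), the standard-labs row, which holds the serum chemistry, is marked at screening, days 7, 14 and 28, and early termination. Day 21 has only the banked-sample draw and the immunology tests.

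**The concern.** The testing interval doubles in the second half of treatment, while the rule that acts on the tests is written as if it did not. Section 7.7 gives drug-induced liver injury special attention, safety is the primary objective, and a clinically significant laboratory value is an adverse event by definition.

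The uncovered case is narrow: a new rise, without symptoms, starting after day 14. Listed symptoms prompt immediate liver chemistries, and a rise above 3x ULN found by day 14 is repeated within 48 to 72 hours. For the uncovered case, the hold and the discontinuation criteria exist on paper but have no dosing left to act on.

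There is a secondary inconsistency. Endpoints 5a and 5b (Section 3.4) ask for day-21 values of markers that include the four liver tests, but Table 1 does not schedule most of those markers that day.

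**Working it through.** The plan gives no figure of its own to reproduce; this is a check of the schedule.

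**Is day 21 really without a liver test?** Three places agree:

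- Section 7.7 names the days and omits day 21.
- The day-21 cell of the Table 1 standard-labs row is empty (read by column position).
- Footnote 12 gives 44 mL on day 7 and 20 mL on day 21. Among the blood rows of Table 1, these days differ only by the standard labs. The difference, 44 − 20 = 24 mL, fits their absence on day 21.

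Footnote 12 also speaks of five collections over five visits, which could be read as every test at every visit. The explicit days in Section 7.7 rule that out for liver tests.

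**Gaps and doses.** Nominal doses are 28 × 3 = 84.

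| Schedule | Gaps (days) | Longest gap | Doses in that gap |
|---|---|---|---|
| Days 1, 7, 14, 28 | 6, 7, 14 | 14 days | 14 × 3 = 42 of 84 |
| Days 1, 7, 14, 21, 28 | 6, 7, 7, 7 | 7 days | 7 × 3 = 21 of 84 |

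**Delay to first detection.** Assume onset uniform over days 14 to 28 and a rise that persists. The mean delay is 14/2 = 7.0 days without a day-21 test and 7/2 = 3.5 days with one. All the gain is in onsets between days 14 and 21; later onsets are first seen on day 28 either way.

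**What can still act on a result:**

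- *First seen on day 28:* the 48 to 72 hour repeat falls on days 28 + 2 to 28 + 3 = 30 to 31, after dosing. No hold or threshold can shorten treatment.
- *First seen on day 21:* the repeat falls on days 23 to 24, on drug. The Section 7.5 hold can act. With the full standard labs, so can three of the four Section 7.7 thresholds, the symptom threshold only through eosinophilia in a symptom-free subject. With the four liver tests alone, only the 8x threshold and the bilirubin arm of the third are supported.
- *Above 5x ULN for more than two weeks:* from day 21 this needs more than 14 further days, that is, beyond day 35. It cannot act in either case.

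**How often?** The documents give no rate. If a proportion p of belnacasan subjects had such a rise between days 14 and 21, the chance of at least one among 20 is 1 − (1 − p)^20. For assumed p of 1%, 5% and 10% this is 18%, 64% and 88%. These show scale only.

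**Endpoints 5a and 5b.** Section 3.4 lists 1 + 8 + 3 + 4 + 1 + 6 + 8 + 11 = 42 markers. Appendix 12.1 groups CD3+ T cells and eight cytokine or inflammasome markers apart from the blood count and chemistry. On that grouping 42 − 9 = 33 markers have no day-21 test: 31 standard-lab markers, viral load and serology. If everything blood-based under the Section 3.4 immunology and inflammation headings counts as immunology tests, 42 − 17 = 25 have none.

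Over five days 5a implies 42 × 5 = 210 marker-by-day values. Viral load also lacks day 7, and serology lacks days 1, 7 and 14. Values with no scheduled test:

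- As planned: 33 + 1 + 3 = 37 (17.6%), or 25 + 1 + 3 = 29 (13.8%) on the wider reading.
- With full standard labs on day 21: 37 − 31 = 6 (2.9%).
- With the four liver tests only: 37 − 4 = 33 (15.7%).

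**The case against.** The strongest reply is that the listed days, the Table 1 row and the blood volume all agree, and only the word for weekly disagrees, so deleting it would restore consistency. The documents also report no liver signal: nearly 100 patients have been treated, at up to 3600 mg/day for up to 13 weeks, and subjects with raised liver tests are excluded at entry. Day 21 keeps a physical examination and symptom review, and an unexplained new symptom holds dosing. A rise that persists to day 28 is still found and, if clinically significant, recorded as an adverse event.

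Much of this stands. The gap is narrow, the primary endpoint is largely preserved, and the assumed rates are not evidence that such rises will occur. Section 7.7 says only that discontinuation will be considered, so a day-21 result would not force a stop. The larger marker count depends on how the immunology tests are grouped, and 5a and 5b can be read as meaning wherever a marker is measured.

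It does not remove the point. Deleting the word would leave half the nominal doses in one gap between liver tests, in a setting where Section 1.3 acknowledges that data on acute viral infection are absent. Symptom checks do not detect a silent rise.

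**Conclusion.** The concern holds. The schedule does not deliver the weekly testing on which Section 7.7 relies, and for a new symptom-free rise after day 14 the dosing safeguards come too late on the routine schedule. A day-21 test would bring detection forward by 7 days (21 nominal doses) for a persistent rise starting between days 14 and 21, and by nothing for later onsets. Testing outside the schedule, such as during a hospital stay, could find a rise sooner.

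This should be changed, but it does not threaten the comparison between arms. The endpoint mismatch is a limited consistency matter: the caspase-1, IL-18, IL-1β and gasdermin D tests are scheduled on day 21.

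**What to change.** Mark the standard labs on day 21 in Table 1, add day 21 to the list in Section 7.7, and update the day-21 volume in footnote 12. ALT, AST, ALP and total bilirubin are the minimum. The full row is better, because two thresholds also use INR or eosinophils, which come from the coagulation and hematology tests and are not part of the 48 to 72 hour repeat.

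The cost is at most 40 panels on an existing visit and draw, and roughly 24 mL or less of extra blood per subject. That volume is approximate because the footnote 12 volumes do not add up by row.

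Smaller corrections to make at the same time:

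- In 5a and 5b, limit each marker to the days it is tested: viral load on days 1, 14 and 28; serology on day 28, plus day 1 if the assay is run on the enrollment serum banked under footnote 5. Otherwise drop the serology change from enrollment.
- Add GGT to the screening chemistry in Appendix 12.1, since Section 5.3 excludes on it.
- Optionally, refer from Section 7.7 to the hold in Section 7.5.
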